3.9.6 Biomarkers

Blood will be drawn at Baseline and Day 84 (week 12) for Biomarker analysis. Analyses will not be performed at this time.

3.9.7 Suicidality

Suicidality is measured by the irritability scale from the ABC-C, also referred to as ABC-I. It is collected at Baseline, day 43 (week 6), and day 84 (week 12), and additionally at Phone Titrate, Phone Safety, Unscheduled, and Follow-up Phone visits. The ABC-I Completed by Clinician assessment described in the protocol consisted of the clinician completing the questionnaire based on the caregiver's response. In the protocol Schedule of Assessments, both ABC-I Clinician and ABC-C Caregiver were noted to be completed during clinic visits. However, in practice during the study, the ABC-I Clinician assessment was often not entered during clinic visits. Since the information is captured in the ABC-C Caregiver assessment, this data will be used to supplement the ABC-I assessment if missing at clinic visits.

Descriptive statistics for the ABC-I subscale and individual item scores will be presented by treatment group for each visit.

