**Investigational Product and Packaging:**

OV101 is supplied as 5 mg capsules, and matching placebo capsules, in bottles. Bottles will have "Morning" or "Evening" printed on their labels. Caregiver will receive a sufficient number of capsules in 1 bottle "Morning" and 1 bottle "Evening" at Baseline and at Week 6 Interim visits.

Depending on the allocated treatment group, the "Morning"/"Evening" bottles will contain:

- Group A (QD): Morning – Placebo/Evening – OV101
- Group B (BID): Morning – OV101/Evening – OV101
- Group C (Placebo): Morning – Placebo/Evening – Placebo

Justification of dose range:

The evening dose was selected based on the safety and efficacy data from all studies conducted by Merck/H. Lundbeck A/S in the indication of insomnia (reference to IND 64,567 from H. Lundbeck A/S).

The morning dose was selected based on a Phase 1 study in healthy volunteers, which determined that a 10 mg morning dose had a similar safety profile to placebo.

The doses of OV101 administered will be the same for adolescent and adult subjects. PK results from the adolescent PK study OV101-16-001 indicate that the PK profile of OV101 following a single 5 mg oral administration to adolescent male and female subjects with Fragile X syndrome (FXS) or AS is comparable to data with the same dose previously obtained from healthy young adult subjects. Therefore, OV101 exposure in the present study is anticipated to be consistent across adolescent and adult subjects. While the same target dosages are planned in adolescent and adult subjects, dosing may be individualized at the investigators discretion based on tolerability through up- and down-titrations as described in Section 12.1.3.

Titration conventions:

Doses will be progressively increased in 5 mg increments (OV101 or placebo) (Table S1) to a target of 15 mg (3 capsules) in the evening and 10 mg (2 capsules) in the morning for each subject, which will deliver the target dose of 15 mg OV101 as an evening dose in Schedules A and B, and 10 mg OV101 as a morning dose in Schedule B. Each dose-escalation will be performed after adequate tolerability has been assessed by caregiver and investigator during a phone visit. Unscheduled study center visits are optional at any time to confirm tolerability.

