15.1 Suicidality

Most individuals with AS are not able to communicate thoughts of suicidality, so subject irritability reported by the caregiver is being used as a surrogate measure of suicidality. The ABC-C Irritability subscale will be used as an indicator for suicidality. The investigator will review the scale items with the caregiver at each scheduled time point. If grading worsens, the investigator must decide whether that indicates a suicidal ideation of the subject, and if so, must document it as an AE and closely monitor it until resolution.

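### The ABC-I fill-in rule lets change from baseline at Weeks 6 and 12 compare a clinician form with a caregiver form in the same subject; one caregiver-form series would avoid this (minor)

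*SAP*

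**What the plan says.** SAP 3.9.7, repeated as a change from protocol in SAP 3.11, reports that "in practice during the study, the ABC-I Clinician assessment was often not entered during clinic visits". Its remedy is that the caregiver ABC-C fills the gap: "this data will be used to supplement the ABC-I assessment if missing at clinic visits". The clinician score thus has priority, and the caregiver score is used only where the clinician score is absent.

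The same section says that the clinician form "consisted of the clinician completing the questionnaire based on the caregiver's response". It also says that the ABC-I is collected at the three main visits and "additionally at Phone Titrate, Phone Safety, Unscheduled, and Follow-up Phone visits".

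For analysis, "Descriptive statistics for the ABC-I subscale and individual item scores will be presented by treatment group for each visit". SAP 3.3.3 makes the safety endpoint the change in ABC-C irritability to every post-baseline assessment, and Table 14.2.2.4 shows both values and changes. Protocol 17.2.3.2 defines the suicidality variable through the ABC-C Irritability subscale at Weeks 6 and 12. SAP 3.1.1 takes as baseline the latest non-missing pre-dose value and does not say from which form.

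**The concern.** A change score is clean when both of its ends are measured in the same way. Here the form at each end depends on whether a clinician record was entered, so some subjects have clinician minus clinician, some caregiver minus caregiver, and some a mixture. Any systematic difference between a form the caregiver completes and one a clinician completes from the caregiver's answers would then enter the change. It would add noise. If the missing share changes between visits, it would also shift the mean change in an arm.

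The visible SAP has no flag for the source of a score, no check of agreement between the forms, no summary on a single form, and no rule for which form supplies the baseline. A reader of Table 14.2.2.4 could not tell a change in irritability from a change of form. The measure matters because it is the trial's only scale-based indicator of suicidality, in a study whose primary objective is safety.

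**Working it through.** The plan states no figure on this point, so there is nothing to reproduce. The check has three parts.

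**1. Is one form available at the main visits?** Protocol Table 1 schedules the caregiver ABC-C at Screening, Baseline, Interim (Day 43) and End of Treatment (Day 84). It is not scheduled at phone or unscheduled visits. SAP 4.1.2 lists 15 items for the irritability factor. The five factors together use 15 + 16 + 7 + 16 + 4 = 58 items, each once, and this matches protocol 14.1.4. Factor I can therefore be scored from the caregiver form at Baseline, Week 6 and Week 12 wherever the form was completed.

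**2. What could mixing do?** Let d be the mean caregiver-minus-clinician difference, and let p0 and p1 be the shares of scores taken from the caregiver form at baseline and later. The documents give none of these; the only information is that the clinician form was missing often. All values below are assumptions. The formulas take d as constant and unrelated to which form is missing.

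- Shift in mean change = d(p1 − p0). This does not need independence across visits.
- Share of subjects with mixed forms = p0(1 − p1) + p1(1 − p0), if form use is independent across visits.
- Added variance of change = d²[p0(1 − p0) + p1(1 − p1)], also under independence.

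| p0, p1 | Mixed share | Mean shift | Added SD |
|---|---|---|---|
| 0.3, 0.3 | 42% | 0 | √0.42 d = 0.65d |
| 0.4, 0.4 | 48% | 0 | √0.48 d = 0.69d |
| 0.2, 0.6 | 56% | 0.4d | √0.40 d = 0.63d |
| 0.5, 0.8 | 50% | 0.3d | √0.41 d = 0.64d |

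With d = 0 every effect is zero. With d = 1 to 3 points, the third row gives a within-arm shift of 0.4 to 1.2 points. Independence matters for the mixed share: if the same subjects lack the clinician form at both visits and p0 = p1, the mixed share is 0% rather than 42% or 48%.

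The between-arm bias is d times the difference between arms in (p1 − p0). It is zero in expectation when the arms have the same shares. If the arms differ by 20 percentage points in that quantity, it is 0.2d, or 0.2 to 0.6 points for d = 1 to 3. With the caregiver form at all three visits for everyone, p0 = p1 = 1 and the shift is d(1 − 1) = 0 for any d.

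**3. What about the other visits?** Only the clinician form is scheduled at the eight phone time points (Days 3, 7, 10, 14, 31, 57, 71 and 98). Those are eight of the ten scheduled post-baseline ABC-I assessments. A caregiver baseline carried to those visits would make every phone-visit change mixed. Under the current rule the same happens to the share p0 whose baseline was filled from the caregiver form, with a mean shift of d(0 − p0) = −p0 d; for p0 = 0.2 that is −0.2d. Unscheduled visits belong with the phone visits, although some take place at the center (protocol 12.1.3.1: "Unscheduled study center visits are optional at any time to confirm tolerability"). Restricting phone and unscheduled change to subjects with a clinician-form baseline removes the mixing and loses the share p0 from those summaries.

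**The case against.** The strongest reply is that the two sources are nearly the same by design. The informant is the caregiver in both, the subscale is the same, and the Screening entry in the clinician row of the schedule already sends the reader to the caregiver score. The sponsor disclosed the substitution in SAP 3.11, and no document shows a systematic difference. Allocation is randomized and blinded, and nothing suggests that missingness differs by arm, so a common shift cancels against placebo. All of this stands, and it is why the point is minor. It does not explain why the form should vary from visit to visit when the schedule provides one that need not.

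A caregiver-only baseline used everywhere would also do harm, as the third part of the working shows. That objection stands too, and it shapes the fix.

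Three stronger readings are tempting but unsupported:

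- A reader might infer that a complete caregiver score exists at every clinic visit. The documents give a schedule but no completion rate, and unscheduled center visits have no caregiver ABC-C.
- A reader might infer that purely descriptive reporting is itself a defect that hides subjects who worsen. Protocol 17.2.3 prescribes descriptive statistics for safety variables. SAP 3.1 includes the maximum and lists all subject data. Under protocol 15.1, "If grading worsens, the investigator must decide whether that indicates a suicidal ideation of the subject", and worsening so judged is recorded as an adverse event. A count of subjects who worsen would be an optional extra.
- A reader might infer that two independent raters are being mixed. The difference is one of form and mode of completion only.

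**Conclusion.** The concern holds in a limited sense. SAP 3.9.7 and 3.11 allow change from baseline at Week 6 and Week 12 to compare different forms within a subject. By schedule this is avoidable with the instrument that SAP 3.3.3 and protocol 17.2.3.2 name.

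The effect cannot be sized from the documents. It is zero if the forms agree. The 0.4 to 1.2 point within-arm shift rests on an assumed form difference of 1 to 3 points and an assumed rise in the caregiver-form share from 20% to 60%. A bias against placebo would further require missingness to move differently between arms, and nothing in the documents suggests that. The documents do not support a claim that the safety comparison is biased. Severity is minor: the change is worth making because it costs little and makes the table interpretable.

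**What to change.** Revise SAP 3.9.7 and 3.11, and the specification of Table 14.2.2.4, as follows:

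1. At Baseline, Week 6 and Week 12, derive the ABC-I from caregiver ABC-C Factor I (SAP 4.1.2) for all subjects. Use the clinician score only where the caregiver form is absent, and flag each such value.
2. At phone and unscheduled visits, summarise the clinician form as observed values. Show change only for subjects with a clinician-form baseline.
3. Where both forms exist at a visit, report their agreement, for example the mean and SD of the paired difference. This supplies the d that the plan lacks.
4. Keep the current fill-in rule as a sensitivity summary.

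The cost is SAP wording and a little programming; no new data are needed. The downside is fewer subjects with a phone-visit change score. At an assumed 20% of clinician baselines missing, that is 0.2 × 25 = 5 subjects per arm of 25.

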3.10 Interim Analysis

3.11 Changes from Protocol

Description of Caregiver:

During development of the study eCRFs, the relationship of the caregiver to the subject was collected in order to identify type of relationship as: parent, grandparent, friend, or other (like a group home resident).

Criteria for Per Protocol Determination:

Prior to database lock and unblinding, there will be a meeting to review protocol deviations. The threshold for percent treatment compliance that would be considered inadequate and would result in exclusion from the per protocol set will be determined in this meeting following review of the relevant compliance information. In the study

protocol 80% treatment compliance was specified as the threshold defining the per protocol exclusion, however, due to the allowance of down-titration in this study, it was determined that treatment compliance cannot be assessed with sufficient accuracy to warrant a strict 80% threshold. A lower threshold may be considered in the abovementioned meeting. If it is decided to lower the compliance threshold, this change will be documented in the CSR.

ABC-I Assessment at Clinic Visits:

The ABC-I is the irritability scale from the ABC-C. The ABC-I Completed by Clinician assessment described in the protocol consisted of the clinician completing the questionnaire based on the caregiver's response. In the protocol Schedule of

Assessments, both ABC-I Clinician and ABC-C Caregiver were noted to be completed during clinic visits. However, in practice during the study, the ABC-I Clinician assessment was often not entered during clinic visits. Since the information is captured in the ABC-C Caregiver assessment, this data will be used to supplement the ABC-I assessment if missing at clinic visits.

The hypothesized treatment effects on efficacy have shifted based on results from related studies that have been reported after the protocol was developed.

Primary Comparisons of Interest:

The protocol states that the primary comparisons of interest are between each active treatment group (dose group) and placebo group. In the SAP, it is determined that the primary comparisons of interest are between the combined OV101 group and placebo, in order to increase statistical power.

4 DATA HANDLING

4.1 Derived Endpoints and Data Handling

4.1.1 Handing of Repeated Assessments

If multiple results are reported for an assessment at the same post-baseline visit, then the first record will be used in analysis.

4.1.2 Aberrant Behavior Checklist-Community (ABC-C)

Five factors are defined as follows:

[figure not shown]
Factor	Sum of Questions
Irritability, Agitation, Crying	2, 4, 8, 10, 14, 19, 25, 29, 34, 36, 41, 47, 50, 52, 57
Lethargy, Social Withdrawal	3, 5, 12, 16, 20, 23, 26, 30, 32, 37, 40, 42, 43, 53, 55, 58
Stereotypic Behavior	6, 11, 17, 27, 35, 45, 49
Hyperactivity, Non Compliance	1, 7, 13, 15, 18, 21, 24, 28, 31, 38, 39, 44, 48, 51, 54, 56
Inappropriate Speech	9, 22, 33, 46

4.1.3

[REDACTED]	[REDACTED]

Gross Total = Sum of Composites

[figure not shown]
4.1.4

4.1.7

4.1.8 EEG

Some of the EEG questions will be combined into one question:

- The 3 back ground questions of mild slowing, moderate slowing and severe slowing will be combined into one questions of Background slowing with 1=Mild, 2=Moderate or 3=severe responses
- The 3 Occipital Rhythm questions of normal for age, slow for age or absent will be combined into one question of Occipital Rhythm with responses of normal for age, slow for age or absent.
- The 2 rhythmic theta questions of <50% of the time and >50% of the time will be combined into one question of Rhythmic theta with responses of 1: <50% of the time or 2: >50% of the time.

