3 STATISTICAL METHODS

3.1 General Methods

All statistical analyses will be performed using SAS® Version 9.4 or higher for Windows.

All clinical study data will be presented in subject data listings. In by-treatment group descriptive presentations, the 3 randomized treatment groups (15 mg evening dose only [QD], 15 mg evening dose plus 10 mg morning dose [BID], placebo) will be presented separately as well as a combined treatment group for OV101 QD and BID dosing.

Descriptive statistics (n, mean, standard deviation, Q1, median, Q3, minimum, and maximum) will be calculated by treatment group for continuous variables. Confidence intervals will be provided where appropriate.

Frequencies and percentages will be presented by treatment group for categorical variables. If there are missing values, the number missing will be presented, but without a percentage.

Means, medians, and confidence intervals will be reported to one decimal place more than the data reported on the Case Report Form (CRF) or by the laboratory/vendor. Standard deviations will be reported to two decimal places more than the data reported. Minimum and maximum will be reported to the same number of decimal places displayed on the CRF or by the laboratory/vendor. P-values will be reported to 4 decimal places.

Unless otherwise specified, all tests will be 2-tailed using a 0.05 level of significance. All confidence intervals (CIs) will be 2-sided 95% CIs.

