3.3.3 Safety Endpoints

- Incidence of adverse events
- Change in clinical laboratory parameters from Baseline to each post-baseline assessment
- Shift in clinical laboratory parameters from Baseline to each post-baseline assessment
- Change in vital sign measurements from Baseline to each post-baseline assessment
- Change in physical exam parameters from Baseline to each post-baseline assessment
- Change in EEG from baseline to the end of treatment
- Change in irritability from ABC-C from Baseline to each post-baseline assessment.
- Clinically important changes in seizure medication from the electronic seizure diary

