3.9.4 EEG

EEG is collected at Baseline and Day 84 (week 12). Occipital rhythm, rhythmic theta, rhythmic delta, epileptiform abnormalities, and sleep will be analyzed descriptively. For occipital rhythm, the categories are normal, slow, or absent, with undeterminable as a response option. For rhythmic theta, the categories are <50% or >50%, with undeterminable as a response option. For these discrete variables, frequencies and percentages will be presented by treatment group for each visit. The sleep-related variables, total time of sleep recording in minutes, time asleep in minutes and percent time asleep will be summarized using descriptive statistics for each visit by treatment group.

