15.5 Electroencephalogram Assessments

EEG will be assessed as changes in background rhythms and the frequency of epileptiform discharges. Study centers will perform a routine EEG with local equipment. EEG should be done towards the end of a visit to minimize any confounding impact on subject performance. Standard protocol and montage will be followed as outlined in the separate EEG manual, including but not limited to resting and evoked stimuli. Placing of electrodes (if possible according to the international 10/20 system) must be documented. Recording should last about 10 minutes in the wake state, and if possible, recording should end with a nap period. Data will be collected in electronic format in European Data Format for centralized reading. An EEG manual will be provided.

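### The EEG safety endpoint is a change from baseline, but no planned table shows within-subject change, and two derived EEG variables have no level for absence

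*SAP*

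**What the plan says.** Safety is the primary objective, and EEG is among the safety endpoints in protocol section 9.1. Protocol section 15.5 states the aim: "EEG will be assessed as changes in background rhythms and the frequency of epileptiform discharges". SAP 3.3.3 words the endpoint as "Change in EEG from baseline to the end of treatment". EEG is recorded twice, at Baseline and at Day 84.

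For the analysis, SAP 3.9.4 says: "Occipital rhythm, rhythmic theta, rhythmic delta, epileptiform abnormalities, and sleep will be analyzed descriptively". For the discrete variables, "frequencies and percentages will be presented by treatment group for each visit". Background slowing is not in that list, although Table 14.3.4.1 covers readability and EEG background. Tables 14.3.4.1 to 14.3.4.6 are all titled as summaries. Laboratory data (SAP 3.9.2, Tables 14.3.2.1.2 and 14.3.2.2.2) and physical examination (SAP 3.9.5, Table 14.3.5.2) have shift tables.

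SAP 4.1.8 merges several EEG questions. Three become "Background slowing with 1=Mild, 2=Moderate or 3=severe responses". Two become a two-level rhythmic theta variable, on which SAP 3.9.4 says: "For rhythmic theta, the categories are <50% or >50%, with undeterminable as a response option". The merged occipital rhythm variable keeps a normal-for-age level. On missing data, SAP 3.1 says: "If there are missing values, the number missing will be presented, but without a percentage". Rule 7 of SAP section 5 adds an Unknown or Missing category to categorical tables.

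**The concern.** There are two separate gaps.

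The first is between endpoint and analysis. A change endpoint concerns what happens to each subject between two recordings, whereas by-visit percentages describe each visit's margin only. If some subjects worsen while others improve, the margins can stay still. In a trial whose primary question is safety, the subjects who worsened are the ones a reader needs to see.

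The second is the coding. Going from no slowing to some slowing is a change that a safety EEG should be able to show. As SAP 4.1.8 is written, a readable recording without slowing has no stated value, and neither does one without rhythmic theta. How such recordings enter the table, and whether they count in the denominator, is left open. One plausible reading of the plan gives percentages that move the wrong way when mild slowing newly appears.

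**Working it through.** The documents give no EEG figure to reproduce. The check sets endpoint against planned output and then works through counts.

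**Step 1. Endpoint against planned output**

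| Safety data | Endpoint in SAP 3.3.3 | Shift table planned? |
|---|---|---|
| Laboratory | change and shift | yes |
| Physical examination | change | yes |
| EEG | change | no |

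The table numbers run unbroken from 14.3.4.1 to 14.3.4.7 (the last is the seizure diary), so no EEG table in that run has been removed from the public copy.

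**Step 2. What by-visit frequencies cannot show**

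Assumption, not from the documents: one arm of 25 (the planned size) with background slowing at baseline of none 10, mild 5, moderate 5, severe 5. Let the five mild subjects become moderate and the five moderate subjects become mild. Day 84 is again 10, 5, 5, 5. Both visits print the same counts and percentages under any denominator. A shift table shows 5/25 (20%) worsened and 5/25 (20%) improved. This step does not depend on how absence is coded.

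**Step 3. Absence treated as missing**

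Further assumption: a recording with no slowing is coded missing, and percentages use non-missing recordings. The baseline denominator is then 5 + 5 + 5 = 15, so each grade is 5/15 = 33.3%. Subjects with slowing at baseline do not change; only the new cases differ.

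| New cases among the 10 with none | Day 84 none/mild/moderate/severe | Denominator | Mild | Moderate | Severe |
|---|---|---|---|---|---|
| 4 mild | 6/9/5/5 | 19 | 47.4% | 26.3% | 26.3% |
| 8 mild | 2/13/5/5 | 23 | 56.5% | 21.7% | 21.7% |
| 4 mild, 3 moderate, 1 severe | 2/9/8/6 | 23 | 39.1% | 34.8% | 26.1% |
| 8 moderate | 2/5/13/5 | 23 | 21.7% | 56.5% | 21.7% |
| 8 severe | 2/5/5/13 | 23 | 21.7% | 21.7% | 56.5% |

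With eight new mild cases, moderate and severe each go from 33.3% to 5/23 = 21.7%, although eight subjects worsened and none improved. With eight new severe cases the worsening shows.

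The size depends on how many recordings show no slowing at baseline. Keep the three grades equal and let half of the none group become mild. With 4 at none, severe goes from 7/21 = 33.3% to 7/23 = 30.4%. With 16 at none, it goes from 3/9 = 33.3% to 3/17 = 17.6%.

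**Step 4. The same data with a none level and all readable EEGs as the denominator**

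Take eight new mild cases and all 25 recordings readable. None goes from 10/25 (40%) to 2/25 (8%) and mild from 5/25 (20%) to 13/25 (52%). Moderate and severe stay at 5/25 (20%). The shift table shows 8/25 (32%) worsened and 0 improved.

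**The case against.** The strongest reply is that the EEG form is not shown. SAP 4.1.8 says that only some questions are combined, and Table 14.3.4.1 covers EEG background, so a separate normal-background item may exist. If the three slowing questions are yes/no items, three negative answers already identify absence. SAP 3.1 states no EEG denominator. All of this stands. A reader might infer that recordings without slowing become missing and that percentages are taken among slowed recordings only, but the documents leave both open.

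The false impression is also limited. Frequencies are printed beside percentages, and a missing row is added. In the eight-mild case a careful reader would see mild rise from 5 to 13, moderate and severe stay at 5, and missing fall from 10 to 2. That trace is real, although a bare missing count would not separate absence from an unreadable or absent recording. A reader might also conclude that the whole derived set lacks a normal level; occipital rhythm has one.

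Finally, all data are listed by subject, detrimental changes in condition are recorded as adverse events (protocol section 16.1.1.2), and seizures have their own table. Individual worsening can therefore be recovered. Listings are nevertheless not a summary of a named endpoint, and none of this answers Step 2.

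**Conclusion.** The point holds in two parts of different strength.

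The first needs no assumption about the form: the SAP names change in EEG as a safety endpoint and plans no table that shows within-subject change. Offsetting worsening and improvement would appear in no planned EEG table.

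The second is conditional. Background slowing and rhythmic theta have no stated level for absence, and SAP 3.9.4 omits background slowing. Percentages that mislead would follow only if absence is treated as missing, those recordings are dropped from the denominator, and the new cases are milder than the existing ones. Under the assumed counts in Step 3, eight new mild cases lower the severe percentage from 33.3% to 21.7%; four lower it to 26.3%. The counts are assumed, and recordings without slowing may be uncommon here, because the protocol describes characteristic abnormal EEG patterns in this syndrome. The documents do not support saying that emergent slowing will look like improvement.

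This is a cheap improvement worth making. No alpha, power or sample-size figure is affected.

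**What to change.** - **SAP 3.9.4 and Tables 14.3.4.1 to 14.3.4.5:** add baseline-by-Day 84 shift tables by arm for the discrete EEG variables, and name background slowing among the variables analysed.
- **SAP 4.1.8:** add a none level to background slowing and to rhythmic theta, derived from the existing EEG items. Keep it distinct from undeterminable, unreadable and missing. If the form has a normal-background item, use it and say so.
- **Denominator:** state that percentages use readable EEGs at the visit, with unreadable and missing recordings counted separately.

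The cost is a few extra tables and a derivation line. No new data are needed, provided absence can be read from the existing items on a readable recording; confirm this against the EEG form before the derivation is fixed.
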